**7.4 For patient who received ibrutinib previously:**

Note: due to the observed ibrutinib withdrawal syndrome in selected CLL patients who had received ibrutinib before, steroid use in the format of 0.5 mg to 2 mg per kilogram body weight prednisone or equivalent is allowed with a gradual taper to overcome the ibrutinib withdrawal syndrome. The duration of high dose steroid use should be within the first 1-3 months when patients were off ibrutinib

**7.5 If CLL or NHL patients have achieved CMR/CR (MRD negative CR for CLL patients) confirmed by bone marrow or CT/PET evaluation, patients could continue the treatment for 2 more cycles and stop the treatment at the discretion of the treating provider. If patient experiences disease relapse after stopping therapy due to CMR/CR, the previous treatments can be restarted. The designed maximum length of active treatment with MK-3475 is 12 or 24 months.**

**7.6 Total duration of treatment including both single-agent and combination therapy is a maximum of 12 months. If the patient remains on cycles with a length of 21 days without treatment delays, this will be 17 cycles total. If the cycle length is increased due to dosing frequency changes or dose delays occur, the number of cycles will be reduced to not exceed 12 months (365 days) of treatment total. NOTE: If patient is continuing to benefit from treatment after 12 months, they may continue to receive treatment up to a total duration of 24 months including both single-agent and combination therapy at**

investigator/sponsor discretion.

7.7 At the end of the trial therapy with MK-3475, signal inhibitor can be continued or stopped at the discretion of the treating physicians.

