## 13.0 Treatment/Follow-up Decision at Evaluation of Patient

NOTE: Per addendum 3, for patients with Richter's transformation, treatment and follow-up decision will be based on the Richter's response criteria.

- 13.1 Arm A and Arm C: If the patient develops progressive disease (not tumor flare) at any time while on single-agent (MK-3475) therapy, or has stable disease without partial remission at the response evaluation at months 3 of the single-agent (MK-3475) therapy, a commercially available signal inhibitor can be added to MK-3475 (remain at the dose 200 mg IV every 3 weeks). If the patient develops PMD/PD at any time during active treatment with the combination of MK-3475 and a signal inhibitor or patient refuses all further study participation including refusal of observation, study treatment will be discontinued and the patient will go directly to EVENT MONITORING. Refer to Section 4.0 for required tests at PMD/PD. Patients will then be followed in event monitoring per Section 18.0.
- 13.2 Arm B : If the patient develops PD at any time during active treatment or patient refuses all further study participation including refusal of observation, study treatment will be discontinued and the patient will go directly to EVENT MONITORING. Refer to Section 4.0 for required tests at PD. Patients will then be followed in event monitoring per Section 18.0.
- 13.3 Patients not progressing on active treatment and tolerating the therapy will continue treatment per protocol for 12 months. If patient is continuing to benefit from MK-3475 treatment after 12 months, they may continue to receive treatment up to 24 months at investigator/sponsor discretion.

13.4 Observation: During observation patients will be seen every 3 months according to the test schedule in Section 4.0 for up to one year. When a subject discontinues treatment, all applicable activities scheduled for the final trial visit should be performed at the time of discontinuation. Any adverse events which are present at the time of discontinuation/withdrawal should be followed in accordance with the safety requirements outlined in Section 10.0 - Assessing and Recording Adverse Events. Patients will discontinue study treatment and go to observation for the following reasons:

- Completion of 12 months or more therapy of MK3475 or combination treatment as determined by investigator/sponsor discretion

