- An unacceptable adverse event that occurs after the patient received at least 2 cycles of treatment, which in the opinion of the Investigator, precludes further trial participation.

13.5 Event Monitoring: Patients will enter event monitoring for the following reasons:

- If the patient develops evidence of PMD/PD (For CLL Arm A and C: PMD/PD on combination therapy; For B-NHL Arm B: PD on MK-3475 single therapy) during treatment or OBSERVATION by examination, blood counts, or imaging as defined in Sections 11.23, 11.4, 11.54 and 11.61, they will be considered to have progressed and will enter EVENT MONITORING. Refer to Section 4.0 for required tests at PMD/PD.

NOTE: Patients whose only evidence of disease recurrence is by sensitive evaluation of MRD will continue under OBSERVATION in accord with standard clinical practice and will NOT be considered PD.

- Subsequent treatment for CLL or NHL
- Failure to return for an evaluation during OBSERVATION
- Patient refusal of further study treatment or noncompliance
- Patient develops an intercurrent illness that precludes further participation, or requires a prohibited concomitant treatment
- The Investigator withdraws the patient in the patient's best interests
- Administrative reasons (e.g., the patient is transferred to hospice care)
- Pregnancy
- An unacceptable adverse event that occurs during cycles 1-2

**Note:** When a subject discontinues treatment, all applicable activities scheduled for the final trial visit should be performed at the time of discontinuation. Any adverse events which are present at the time of discontinuation/withdrawal should be followed in accordance with the safety requirements outlined in Section 10.0 -Assessing and Recording Adverse Events

13.6 A patient is deemed ineligible if after registration, it is determined that at the time of registration, the patient did not satisfy each and every eligibility criteria for study entry. The patient will go directly to the event-monitoring phase of the study:

- If the patient received treatment, all data up until the point of confirmation of ineligibility must be submitted. Event monitoring will be required per Section 18.0 of the protocol.
- If the patient never received treatment, on-study material and the End of Active Treatment/Cancel Notification Form must be submitted. No further data submission is necessary.

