16.3 Analysis Plan (to be evaluated in each arm independently)

16.31 Primary Outcome Analyses:

16.311 Definition: The primary endpoint of this trial is the proportion of patients who achieve a confirmed response to single-agent MK-3475. A confirmed response is defined to be a PR, nPR, CCR, CRi or CR (Arms A and B) or PMR, CMR, PR or CR (Arm C) noted as the objective status at any time while on single-agent MK-3475. All patients meeting the eligibility criteria who have signed a consent form and have begun treatment will be evaluable for response, with the exception of patients determined to be a major violation. For CLL patients with Richter's transformation, confirmed response is determined by response criteria defined for Richter's transformation.

16.312 Estimation: In each arm, the proportion of successes will be estimated by the number of successes divided by the total number of evaluable patients in that arm. Exact binomial confidence intervals for the true success proportion will be calculated. In addition, the confirmed response rate for all Richter's transformation patients (9 patients from Arm A and all patients in Arm C) will be calculated.

16.32 Secondary Outcome Analyses (to be evaluated in each arm independently; Arm C analyses may include the 9 Richter's transformation patients from Arm A): (For all outcomes associated with combination therapy in Arms A and C, disease measurements obtained after the last cycle of single-agent therapy are set as the baseline measurements for combination therapy).

16.321 Progression-free survival (PFS) for single-agent MK-3475 is defined as

the time from registration to the earliest date of documentation of disease progression while on single-agent MK-3475 or death due to any cause. In Arm A and Arm C, patients who initiate combination therapy for stable disease after 3 months of single-agent MK-3475 will be censored on the date that combination therapy is initiated.

In Arm A and Arm C, PFS for the combination of MK-3475 and the signal inhibitor is defined as the time from initiation of treatment with the combination therapy to the earliest date of documentation of disease progression while on combination therapy or death due to any cause.

The distribution of progression-free survival will be estimated using the method of Kaplan-Meier.

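### Section 16.321, as worded, counts progression as a PFS event only on treatment but counts death at any time, and it has no censoring rule for patients who stop without progression

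*Combined protocol and SAP*

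**What the plan says.** Section 16.321 starts single-agent PFS at registration and ends it at "the time from registration to the earliest date of documentation of disease progression while on single-agent MK-3475 or death due to any cause". In Arms A and C, combination PFS runs from the start of the combination to "the earliest date of documentation of disease progression while on combination therapy or death due to any cause". The one censoring rule is this: "In Arm A and Arm C, patients who initiate combination therapy for stable disease after 3 months of single-agent MK-3475 will be censored"; the start of the combination is the censoring date. Kaplan-Meier is the estimator, and no general censoring date is given.

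Other sections bear on what happens after treatment stops:

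- Sections 7.1, 7.5 and 7.6 set a 12-month treatment length, extendable to 24 months, and allow an earlier stop after complete remission. Section 7.5 adds: "If patient experiences disease relapse after stopping therapy due to CMR/CR, the previous treatments can be restarted".
- Section 7.7 says that when MK-3475 ends, the "signal inhibitor can be continued or stopped at the discretion of the treating physicians".
- Section 13.4 sends to observation patients who complete treatment or stop for an adverse event after at least 2 cycles: "During observation patients will be seen every 3 months according to the test schedule in Section 4.0 for up to one year". Section 13.5 sends to event monitoring those whose adverse event falls in cycles 1–2 and those who refuse further treatment.
- Section 13.5 describes progression as ("For B-NHL Arm B: PD on MK-3475 single therapy) during treatment or OBSERVATION") and says of such patients that "they will be considered to have progressed and will enter EVENT MONITORING".
- Section 18.1 collects event-monitoring forms every 6 months until progression or subsequent treatment, then every 12 months, up to 4 years from registration.

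**The concern.** The definition is asymmetric. A patient who stops without progression and later dies has a PFS event. A patient who stops and later progresses does not, and stays at risk until death or the end of follow-up. The protocol creates such patients by design, through its treatment limit and its optional stop in remission.

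Two provisions make the end of the on-treatment period harder to locate. Under 7.5, a relapse off drug followed by restarted treatment would literally not count, and only a later progression on the restarted drug would. Under 7.7, it is unclear whether a patient who continues the signal inhibitor alone is still on combination therapy.

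At stake is the meaning of a stated secondary endpoint (goals 2.22 and 2.25), which also enters the biomarker Cox models in 16.331. Two analysts could follow 16.321 in good faith and draw different curves from the same data.

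**Working it through.** **Step 1: set the definitions side by side.** The plan states no PFS rate, median or event count, so there is no figure of its own to reproduce.

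| Endpoint | Progression or relapse off treatment |
|---|---|
| PFS (16.321) | Not counted, as worded |
| Duration of response (16.325) | Counted; ends at first documented relapse |
| TFS and TNT (16.322, 16.323) | End at next treatment; phases separated by naming the combination start, with no *while on* limit |
| Follow-up status (13.5) | Counted during treatment and observation |

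Read literally, a responder who relapses in observation has a duration-of-response event but no PFS event.

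**Step 2: size under assumed rates.** All rates here are assumptions: exponential times; progression median 9, 12 or 18 months; death before progression median 60 months; death after progression median 12 or 60 months. Let h = ln 2 / progression median, d = ln 2 / 60 and p = ln 2 / post-progression death median.

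- PFS counting all progression: S(t) = exp(−(h+d)t).
- Literal PFS at 24 months if everyone progression-free stops at month 12: S(12) × A(12). Here A(t) is the chance of being alive t months after stopping: A(t) = exp(−(h+d)t) + h/(h+d−p) × [exp(−pt) − exp(−(h+d)t)].

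Example with median 12: h = 0.0578 and d = 0.0116, so S(12) = 0.435 and S(24) = 0.189. With p = d, A(12) = 0.5^(12/60) = 0.871, and the literal value is 0.435 × 0.871 = 0.379. With post-progression death median 12, A(12) = 0.759, and the literal value is 0.330.

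| Progression median (months) | Progression-free at 12 months | Of 23 | 24-month PFS, all progression | Literal, all stop at 12 | Gap, points | Gap if half stop |
|---|---|---|---|---|---|---|
| 9 | 0.345 | 7.9 | 0.119 | 0.253–0.301 | 13–18 | 7–9 |
| 12 | 0.435 | 10.0 | 0.189 | 0.330–0.379 | 14–19 | 7–9 |
| 18 | 0.548 | 12.6 | 0.301 | 0.434–0.477 | 13–18 | 7–9 |

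If a quarter stop, the gap is 3–5 points. Progressions left uncounted in months 12–24 when all stop are 23 × h/(h+d) × [S(12) − S(24)] = 4.5, 4.7 and 4.4.

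**Step 3: vary the cap.** A simulation used other assumptions: progression median 6, 12 or 24 months; survival median 36 or 72 months; independent times; 4-year follow-up.

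| Treatment cap | 24-month gap, no early stopping | 24-month gap, 25% stopping early by month 12 |
|---|---|---|
| 24 months | About 0, since nobody is off treatment before month 24 | 7–11 points |
| 12 months | 12–20 points | 16–24 points |

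**Step 4: Arms A and C, single agent.** Assume 40% progress or die by month 3, 30% switch for stable disease and are censored, and 30% respond with a further median of 12 months. Then 0.30 × 0.5^(9/12) = 0.178 remain at risk at month 12, about 4 of 23 or 3 of 17. The 24-month gap is 10–13 points if all stop and 5–7 if half do.

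**Step 5: compare with sampling error.** Section 16.13 gives 3.0 years of accrual and analysis at 3.5 years. If accrual is uniform, follow-up runs from 6 to 42 months, and (42 − 24)/36 = 50% can be followed past 24 months. Under the Step 2 rates, the simulated 95% half-width at 24 months is 18–22 points for 23 patients. Multiplying by √(23/17) = 1.16 gives about 20–25 for 17.

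**Step 6: censor at treatment stop instead.** Assume half the patients have progression median 24 months and half 6. True 24-month PFS is (0.5 × 0.5 + 0.5 × 0.5⁴) × 0.5^(24/60) = 0.213. The estimate is 21% if stopping is unrelated to prognosis, 13–16% if 80–90% of the good-prognosis and 10–20% of the poor-prognosis patients stop, and 24–25% if reversed. This bias can go either way.

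**The case against.** The strongest reply is that *while on* names a phase, not current dosing. Section 16.311 uses the same words for response, yet section 11.0 and note 1 to table 4.1 allow response to be evaluated 2–8 weeks after the last therapy. Section 13.5 attaches the single-therapy label to progression in observation, for Arm B too. Sections 11.236 and 11.546 send the confirmed progression date to the event-monitoring form. An analyst who reads the whole protocol may well count these events, and the questions raised by 7.5 and 7.7 then largely fall away.

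That reading is plausible but does not settle the matter. TFS and TNT separate the phases without the phrase, duration of response has no such limit, and Arm B has no combination phase to separate from. The missing censoring rule remains under either reading.

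The other objections stand in part. Every rate above is assumed, and the largest gaps need treatment to stop at or before month 12. Off-treatment relapse would still appear through duration of response and, once treatment follows, TFS and TNT. The endpoint is a descriptive single-arm curve with no test.

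A reader might infer that the trial will discard off-treatment progression and report PFS inflated by a known amount. The documents support neither step: the intent is unclear, and no progression, death or stopping rates are given.

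**Conclusion.** The point holds as a defect of wording that should be fixed. Followed literally, 16.321 omits first progressions after treatment stops, counts later deaths, and so biases PFS upward. It also leaves patients who stop without progression with no censoring rule.

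The size cannot be determined from the documents. Under the assumed rates, the 24-month gap is about 0 with a 24-month cap and no early stopping, and roughly 13–19 points if every progression-free patient stops at month 12. The latter is about the sampling error of arms of 17–23 patients, but it always favours the drug. Early stopping on top of a 12-month cap reached 24 points in one assumed scenario.

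The response-rate decision rules, their error rates and the sample sizes are untouched.

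**What to change.** In 16.321:

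- Replace both *while on* clauses with first documented progression or death from any cause, on or off treatment. Count from registration for the single-agent phase (before any start of combination) and from combination start for the combination phase. The relapse described in 7.5 then counts when first documented, and the 7.7 question no longer matters for PFS.
- Censor patients without an event at their last disease assessment.
- State one rule for non-protocol therapy started before progression: either censor at the last assessment before it or count later progression, with the other as a sensitivity analysis.
- Keep the stable-disease-switch censoring in Arms A and C.

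**Cost.** No new visits or data are needed. Off-treatment progression will be dated less precisely. Observation visits are 3-monthly, and tables 4.1 and 4.2 schedule no CT in the observation column, although Arm B progression is mainly CT-based. Forms are then 6-monthly, and 12-monthly after subsequent treatment. PFS will probably look less favourable than under the literal reading. If the sponsor already means to count off-treatment progression, the change only writes that down.

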16.322 Treatment-free survival (TFS) for single-agent MK-3475 is defined as the time from registration to the date of initiation of subsequent treatment for CLL/SLL or lymphoma or death due to any cause. In Arm A and Arm C, the initiation of combination therapy with MK-3475 and the signal inhibitor will be considered subsequent treatment.

In Arm A and Arm C, TFS for the combination of MK-3475 and the signal inhibitor is defined as the time from initiation of combination therapy to the date of initiation of subsequent treatment for CLL/SLL or death due to any cause.

The distribution of treatment-free survival will be estimated using the method of Kaplan-Meier.

16.323 The time to next treatment (TNT) for single-agent MK-3475 is defined as the time from registration to the date of initiation of subsequent treatment for CLL/SLL or lymphoma. In Arm A and Arm C, the initiation of combination therapy with MK-3475 and the signal inhibitor will be considered subsequent treatment.

In Arm A and Arm C, TNT for the combination of MK-3475 and the signal inhibitor is defined as the time from initiation of combination therapy to the date of initiation of subsequent treatment for CLL/SLL.

The distribution of time to next treatment will be estimated using the method of Kaplan-Meier.

16.324 The complete response rate will be estimated by the number of patients who achieve a CRI or CR (Arms A and B) or CMR or CR (Arm C) divided by the total number of evaluable patients. Complete response rate will be evaluated for single-agent MK-3475 in each arm and also for the combination of MK-3475 and the signal inhibitor in Arm A and C. All evaluable patients will be used for this analysis. Exact binomial 95% confidence intervals for the true complete response rate will be calculated in each arm.

16.325 Duration of response (DR) is defined for all evaluable patients who have achieved a PR, nPR, CCR, CRI, or CR (Arms A and B) or PMR, CMR, PR or CR (Arm C) as the date at which the patient's objective status is first noted to be a PR, nPR, CCR, CRI, or CR (Arms A and B) or PMR, CMR, PR or CR (Arm C) to the earliest date relapse is documented. Duration of response will be evaluated for single-agent MK-3475 in each

arm and also for the combination of MK-3475 and the signal inhibitor in Arm A and C. The distribution of duration of response will be estimated using the method of Kaplan-Meier.

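### Read literally, Section 16.321 counts progression as a PFS event only on treatment, so progression after treatment ended without progression is not an event

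*Combined protocol and SAP*

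**What the plan says.** Section 16.321 runs single-agent PFS from registration to "the earliest date of documentation of disease progression while on single-agent MK-3475 or death due to any cause". For Arms A and C a second PFS runs from the start of combination therapy to "the earliest date of documentation of disease progression while on combination therapy or death due to any cause". In both, death has no on-treatment limit and progression does. The only censoring rule is for Arms A and C: "patients who initiate combination therapy for stable disease after 3 months of single-agent MK-3475 will be censored" on the date combination starts. Both distributions are estimated by Kaplan-Meier.

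Patients can leave treatment without progression by planned routes: completing 12 months or more, an unacceptable adverse event after at least 2 cycles (both 13.4), or an optional stop in complete response (7.1, 7.5 and the schemas). Section 13.4 then provides: "During observation patients will be seen every 3 months according to the test schedule in Section 4.0 for up to one year". Section 13.5 covers, for Arm B, "PD on MK-3475 single therapy) during treatment or OBSERVATION by examination", blood counts or imaging, and says of patients with such progression that "they will be considered to have progressed and will enter EVENT MONITORING". The follow-up table in 18.1 asks for event-monitoring forms every 6 months until progression or subsequent treatment, up to 4 years after registration.

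The neighbouring endpoints are not limited to time on drug. Duration of response (16.325) runs "to the earliest date relapse is documented". Treatment-free survival for single-agent MK-3475 (16.322) is "the time from registration to the date of initiation of subsequent treatment for CLL/SLL or lymphoma or death due to any cause". Time to next treatment (16.323) has the same structure without death.

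**The concern.** The trial plans for patients to come off drug without progression and keeps following them for progression. The PFS definition then has no place for what that follow-up finds. Take an Arm B responder who completes 12 months, relapses in observation and starts new therapy. That patient has an event for duration of response, treatment-free survival and time to next treatment, but none for PFS unless death follows. A patient who stops in complete response, relapses and is restarted under 7.1 or 7.5 would have PFS dated to a later progression on the resumed drug, with the first relapse skipped.

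PFS is a secondary endpoint in single-arm cohorts, so a reader has no concurrent control against which such an effect would cancel. The same variable enters the Cox models for PD-1, PD-L1 and PD-L2 in 16.331. Because 16.321 also gives no censoring rule for the end of treatment, two analysts could produce different curves from the same data.

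**Working it through.** The plan states no PFS target, event count or power, so there is no figure of its own to reproduce. The check compares the texts and then sizes the effect.

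**Texts side by side, for a relapse in observation after treatment ended without progression**

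| Section | Is the relapse counted? |
|---|---|
| 16.321, PFS | Not on a literal reading; only death can still count |
| 16.325, duration of response (responders) | Yes, at documented relapse |
| 16.322 and 16.323 | Yes, once new treatment starts |
| 13.5 | Yes, as progression, for Arm B and for Arm A/C patients on combination |
| 18.1 | Followed until progression or subsequent treatment |

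No section extends the PFS event to observation or event monitoring.

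**Step per uncounted relapse.** Inputs: 23 evaluable patients in Arm A or B and 17 in Arm C (16.12). With no earlier censoring, Kaplan-Meier PFS is the proportion still event-free, so leaving out one event raises the later curve by 1/n (until that patient's death, if the patient is kept at risk).

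- Arm A or B: 1/23 = 4.3 points.
- Arm C: 1/17 = 5.9 points.
- Arm C with the 9 Arm A Richter's patients that 16.32 allows: 1/(17+9) = 1/26 = 3.8 points.

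For combination PFS the denominator is the number who start combination, which is not given.

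**Illustration without earlier censoring (assumed data, Arm B, n=23).** Fifteen progress on drug by month 6, 8 complete 12 months, 1 of the 8 relapses at month 18, and nobody dies. PFS at 24 months is:

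- relapse counted: 7/23 = 30.4%;
- relapse ignored, or patient censored at relapse: 8/23 = 34.8%;
- all 8 censored at month 12 when treatment stops: nobody is at risk after month 12, so the data give no estimate at 24 months.

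**Illustration with earlier censoring (assumed data, Arm C, n=17).** Six progress before month 3, 3 are censored at month 3 on starting combination for stable disease, 4 progress at month 8, 4 stop without progression, and 1 of these relapses at month 18.

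- Not counted: 11/17 × 4/8 = 32.4%.
- Counted: 11/17 × 4/8 × 3/4 = 24.3%.
- Difference: 8.1 points, more than 1/17, because censoring had reduced the risk set.

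**Sensitivity to the progression rate (assumptions not in the documents).** Exponential time to progression with median m months, all treatment stopping at month 12, no deaths, and patients kept at risk with later progression ignored. True 24-month PFS is 2^(−24/m). The literal rule reads 2^(−12/m). The share of progressions not counted is (2^(−12/m) − 2^(−24/m)) / (1 − 2^(−24/m)).

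| Median m | True | Literal | Share not counted |
|---|---|---|---|
| 6 | 6% | 25% | 20% |
| 12 | 25% | 50% | 33% |
| 24 | 50% | 71% | 41% |
| 36 | 63% | 79% | 44% |

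**Exposure window.** For a patient who completes therapy and is not restarted, 48 − 12 = 36 or 48 − 24 = 24 months of the 4-year follow-up could contain an uncounted progression. These are maxima: scheduled observation lasts up to one year, and the six-monthly progression follow-up ends at subsequent treatment.

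**The case against.** The strongest reply is that *while on* labels the phase. Arms A and C have two PFS clocks in sequence, and some phrase must assign a progression to one of them. Section 13.5 itself speaks of progression *on* a therapy for events found during treatment or observation. The primary endpoint (16.311) uses the same phrase for response, yet 4.1 and 11.1 schedule response evaluation 2 to 8 weeks after the last dose for patients who stop early. A strictly literal reading would sit badly with that.

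This stands as evidence about intent, so a deliberate exclusion of off-drug progression should not be inferred. It does not settle the text. Section 13.1 uses almost the same words about single-agent therapy to mean on drug, since a signal inhibitor is then added to ongoing MK-3475. Arm B is under the same definition with no second phase to separate.

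Two further objections also stand. The upward shift depends on a convention that 16.321 leaves open; censoring at treatment stop would leave later PFS uninformed instead. And the wording of 13.5 names Arm A/C progression on combination and Arm B progression on single-agent therapy, so its direct conflict with 16.321 does not extend to an Arm A/C patient who stopped single-agent MK-3475 and relapsed in observation. For that patient the mismatch is with 18.1 and the other endpoints.

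**Conclusion.** The point holds as a defect in the stated PFS definition. As written, it leaves out progressions that the trial collects, makes PFS inconsistent with the endpoints beside it, and does not say how patients are handled when treatment ends. It should be corrected. Confidence is high about the text and lower about intent.

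The size is conditional. If affected patients stay at risk or are censored at relapse, each uncounted relapse lifts later PFS by 4.3 points at n=23 or 5.9 at n=17 with no earlier censoring, and by more with it. If they are censored at treatment stop, PFS beyond that time is uninformed by them. The number of such patients is not given, and the event counts and progression rates in the illustrations are assumed.

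A reader might infer that reported PFS will be overstated. The documents do not support that: neither the number affected nor the censoring convention is given, and the analysts may intend the phase-label reading. A reader might also infer that the primary result is compromised because 16.311 shares the phrase. The decision rules rest on counts of responders, not on PFS, and this point does not concern them. What is affected is the secondary PFS estimates and the PFS Cox models in 16.331.

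**What to change.** In 16.321, define the single-agent PFS event as the first documented progression or relapse after registration, whether during single-agent treatment, observation or event monitoring, before combination or other new CLL or lymphoma therapy, or death from any cause. Then:

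- keep the existing censoring at combination start for stable disease;
- censor patients who start other new therapy without progression at their last disease assessment before it, since 18.1 ends the six-monthly progression follow-up at subsequent treatment;
- apply the parallel rule to combination PFS;
- for patients restarted under 7.1 or 7.5, use the date of the first relapse.

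If *while on* was only a phase label, this wording makes that explicit. Event monitoring must be named because 13.5 sends some patients there directly without progression, for example after refusal of treatment or withdrawal by the investigator.

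The cost is analysis wording only. Sections 11.236 and 11.546 already direct the date of first progression to the event monitoring form, and 18.1 already schedules the follow-up, so no visits, tests or patients are added. Stopping the count at new therapy is a choice of what PFS measures and should be stated as one. The reported PFS may become slightly less favourable.
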